(5) Patients with serious difficulties in communication or intellectual deficit that impedes the ability to understand the intervention.

Reasons for the participant to be discontinued from the study:

- (1) Withdrawal of informed consent.
- (2) Non-attendance at the study visits (≥ 2 nutritional interventions),
- (3) Exclusion criteria found after enrollment, and
- (4) Any serious adverse event during the intervention period (based on data safety monitoring).
- (5) Admission to dialysis

Figure 1. CONSORT Flow Diagram

Sample size calculation

For the calculation of sample size, the formula was used to compare means of independent samples. A size of 27 patients per group was estimated, considering an expected difference in the Glycated Hemoglobin percentage of 0.7 reported in a previous study (6).

Randomization

Randomization was performed using the simple method without replacement with sealed envelopes. Recruited individuals will be allocated into one of two groups:

- (1) Teleconsultation ($n = 26$)
- (2) Face to face consultation ($n = 27$)

DIETARY INTERVENTIONS

The teleconsultation group received nutritional therapy by video call in real time, with a monthly frequency for 4 months. The consultation includes the evaluation or reevaluation, diagnostic treatment and educational approach. Failure to attend more than two consultations is considered an exclusion criterion.

The Face to face consultation group, received nutritional therapy through face-to-face consultations in the hospital with a monthly frequency for 4 months. The consultation includes the evaluation or re-evaluation, diagnosis, treatment and educational approach. Failure to attend more than two consultations is considered an exclusion criterion.

DATA ANALYSIS PRINCIPLES

To determine the difference between the nutritional interventions, the following changes from the baseline (I1) to the end of the study (I6) will be determined as primary outcomes:

- (1) Renal function with de the determination of the changes in the estimated glomerular filtration rate (eGFR)
- (2) Glycemic control with the determination of the changes in the Hemoglobin A1c (HbA1c)

To evaluate the adherence to nutritional interventions were determined as secondary outcome:

- (1) Level of compliance, was assessed using a self-reported Likert scale. Being the score 10 = good adherence and the score 1 = poor adherence to treatment.

STUDY PROCEDURES

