Data collection

The following clinical/dietary information was obtained:

- Socio-demographic data (a questionnaire).
- Dietary habits: a 3-day food record.
- Vital signs: blood pressure.
- Anthropometric measures: weight, height, body mass index (BMI).
- Gastrointestinal symptoms: frequency and duration.

In the blood serum, we evaluated markers of glucose, and hemoglobin A1c; serum creatinine, urea, albúmin and blood biometry.

STATISTICAL ANALYSIS PLAN

Categorical variables are presented as numbers and percentages, and comparisons between groups were performed with the chi-square or Fisher exact test as appropriate. According to

the Shapiro–Wilk test for data distribution, continuous variables are summarized as the means \pm standard deviations (SD) if normally distributed or medians and interquartile ranges (25–75th) if non-normally distributed and were compared using Student’s t-test or the Mann–Whitney U test, respectively. For variables measured at multiple time points, repeated measures analysis of variance tests were used for the comparisons between groups. For the analysis of the interaction or intervening variables, a stratified statistical analysis will be carried out, using contingency tables and the Mantel-Haenszel method. All tests were two-tailed, and a p value less than 0.05 were considered significant. Statistical analysis and graphics were performed with IBM® SPSS® Statistics Ver. 22).

ETHICS APPROVAL AND CONSENT TO PARTICIPATE

The trial was conducted in accordance with the principles of the Declaration of Helsinki and the International Conference on Harmonization Guidelines for Good Clinical Practice. All patients gave their written informed consent before any study-related procedure. The study was approved by the local ethics committee (14 CEI 14 039 048), was prospectively registered in clinicaltrials.gov (NCT03344549). No funding was received to conduct this study. The clinical trial was carried out under the CONSORT guidelines.

Informed consent was obtained from all subjects. All methods were carried out in accordance with relevant guidelines and regulations. All experimental protocols were approved by the Institutional Review Board “Comité de ética en Investigación del OPD Hospital Civil de Guadalajara [name]”

CONSENT FOR PUBLICATION

REFERENCES

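### The SAP does not fix one test for the two primary outcomes: one rule lets a Shapiro–Wilk result choose between a comparison of means and a rank test, another points to repeated measures ANOVA

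*Combined protocol and SAP*

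**What the plan says.** Three places bear on the primary test.

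- **Data Analysis Principles** defines the primary outcomes as changes in eGFR and HbA1c: "the following changes from the baseline (I1) to the end of the study (I6) will be determined as primary outcomes". It names no test.
- **Statistical Analysis Plan** starts from "the Shapiro–Wilk test for data distribution, continuous variables are summarized as the means" when data are normal, with medians and interquartile ranges otherwise. It closes the sentence with "non-normally distributed and were compared using Student’s t-test or the Mann–Whitney U test, respectively". The following sentence reads "For variables measured at multiple time points, repeated measures analysis of variance tests were used for the comparisons between groups" and carries no normality condition. Alpha is 0.05, two-sided.
- **Sample size calculation** states that "the formula was used to compare means of independent samples" and reaches 27 per group, "considering an expected difference in the Glycated Hemoglobin percentage of 0.7".

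Table 1 marks blood measurements at two times. The plan gives no threshold for Shapiro–Wilk and does not say whether it is applied to levels or changes, by arm or pooled.

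**The concern.** A change score is one value per patient, so it fits the Shapiro–Wilk sentence. The same outcome is also a variable measured twice, so it fits the ANOVA sentence. Which rule governs can therefore be settled after the data are seen.

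The routes do not all answer the same question. Student's t compares mean change. Mann–Whitney asks whether values in one arm tend to be larger than in the other, and here it would be reported with medians. If the gate fires for one primary outcome and not for the other, the two would be judged on different hypotheses and effect measures. For HbA1c, a rank result would not address the mean difference on which the trial was sized.

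**Working it through.** **1. The planned size.** With n = 2(z₀.₉₇₅ + z_power)² SD² / δ², δ = 0.7 and n = 27, the implied SD is 0.7 × √(27 / (2 × (1.960 + 0.842)²)) = 0.92 at 80% power. It is 0.79 at 90% power. The plan states neither SD nor power, so 27 can be matched but not verified. The formula is in any case one for means.

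**2. The ANOVA route.** Let d be each patient's change. With two times, the group-by-time contrast is the difference between arms in mean d, and F(1, 51) = t², where 51 = 26 + 27 − 2. On this reading the test is already Student's t on change and Shapiro–Wilk plays no part.

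**3. The Shapiro–Wilk route.** Assumed rule: Mann–Whitney if Shapiro–Wilk gives p < 0.05 in either arm, otherwise Student's t. Arms have 26 and 27 patients, with 2,000 to 10,000 simulated trials per scenario. At 3,000 trials the standard error of a rate of 26% is √(0.26 × 0.74 / 3,000) = 0.8 points.

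*How often the gate fires on exactly normal data:* 1 − 0.95² = 9.75%; simulated, 10%.

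*Both arms the same shape, no difference (false positives, t / switch):* normal 4.6% / 4.8%; t with 3 df 4.8% / 5.3%; lognormal with sigma 0.5, 4.9% / 5.3%.

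*A responder subgroup in one arm only.* Its mean change is 0.7 in every row (0.20 × 3.5 = 1/3 × 2.1 = 0.5 × 1.4 = 0.7). The other arm has normal changes, with mean zero in the power column and mean 0.7 in the equal-means column.

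| Responders × fall, residual SD | Power for 0.7, t / switch | Rejection with equal means, t / switch |
|---|---|---|
| 20% × 3.5, SD 0.7 | 55% / 26% | 6% / 28% |
| 20% × 3.5, SD 0.92 | 45% / 28% | 5.9% / 14% |
| One third × 2.1, SD 0.7 | 73% / 65% | 5.0% / 6.7% |
| Half × 1.4, SD 0.7 | 83% / 82% | 5.5% / 5.8% |

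*Equal means, normal against lognormal arm (sigma 0.5 to 1.0):* switch 7.1% to 9.0%, t about 5.4%. Arms skewed in opposite directions, an extreme case, give 30% to 50% for the switch, but t itself is then at 7.4% to 10.3%.

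*Same shape in both arms plus a true shift of 0.7 (power, t / switch):*

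- Lognormal, sigma 0.5: 78.7% / 90.8%, a gain of 12.1 points for the switch.
- t with 3 df: 82.6% / 93.6%, a gain of 11.0 points.
- 20% large responders in both arms: 34% / 60%, a gain of 26 points.

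**4. The unstated details matter.** With 35% of one arm falling by 2 points, power is 72.6% for t, 67.4% for the switch gated by arm, and 60.5% gated on pooled data. The choice left open is worth 67.4 − 60.5 = 6.9 points.

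**The case against.** The strongest reply is that the gate may never reach the primary outcomes. The ANOVA sentence can be read to cover them, and on that reading a mean-based test is already planned. This stands. A reader might infer that Shapiro–Wilk decides the primary test; the documents do not settle that. The reply does not remove the defect, because no sentence ties either rule to change in eGFR or HbA1c.

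Second, the large figures come from an invented and extreme shape: one fifth of a single arm falling by five residual SDs (3.5 / 0.7). This also stands. The documents give no distribution, and milder shapes shrink the effect to a few points or nothing. The 0.05 gate applied by arm is likewise an assumption.

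Third, both arms receive monthly therapy with the same components and only the delivery differs, so similar shapes in both arms are plausible. In that case the switch keeps its error rate and gains power. This stands, and it belongs in the cost of the fix.

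Fourth, a reader might infer that the switch manufactures false positives. With identical distributions it does not. With equal means and different shapes, Mann–Whitney detects a real difference in distribution, and the plan pairs it with medians. The error arises only if that result is read as a difference in mean change, the quantity behind the sample size.

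**Conclusion.** The point holds as a failure to fix one primary test. One available route makes the hypothesis depend on the data, and it can lead away from the mean difference that the trial was sized to detect. The documents do not support the stronger claim that the gate certainly governs the primary comparison, nor that it inflates error in general.

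The size is conditional. For a responder subgroup confined to one arm, rejection under equal means ranges from about 6% to 28%, and power for a 0.7 difference from practically unchanged (82% against 83%) to roughly halved (26% against 55%). With a common shape, error stays near 5%. These figures rest on assumed SDs, shapes and gate. What does not depend on them is that the plan allows different tests of different quantities for the same outcome. This is a cheap improvement.

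**What to change.** In the Statistical Analysis Plan:

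- Name one mean-based primary analysis for both outcomes, whatever Shapiro–Wilk shows. Examples are a linear model of the final value adjusted for baseline, or a Welch t-test on change. Report the difference between arms with its 95% CI.
- State that neither the Shapiro–Wilk rule nor the ANOVA sentence provides an alternative primary test.
- Report Mann–Whitney with the Hodges–Lehmann shift as a named sensitivity analysis.
- Keep Shapiro–Wilk only for choosing between mean (SD) and median (IQR) in descriptive tables.

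The cost is wording; no further data are needed. The downside is lost power if changes are heavy-tailed or similarly skewed in both arms, about 11 to 26 points in the examples above. The sensitivity analysis would show this.

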Clinical study protocol

Effect of the Teleconsultation of Renal Nutrition on Renal Function and Glycemic Control in Patients With DKD

Protocol number: NCT03344549

Date: 30 october 2022

INTRODUCTION

Diabetic kidney disease (DKD) is the leading cause of end-stage renal disease(1). The progression of diabetic nephropathy can be delayed by optimal glycemic control. Nutritional therapy with sugar control and low protein diets (0.8 g/kg/day) are the most recommended (2) however, it is difficult to achieve compliance (3). The dimensions of chronic kidney disease show it as a public health problem that requires the creation of new interventional and educational programs (4). Telehealth may improve clinical outcomes, care coordination, engagement, and satisfaction.

METHODS

Primary objective

The main goal of the study, a randomized and controlled study, is to determine a difference between the nutritional intervention through teleconsultation and the face-to-face consultation in patients with diabetic kidney disease in stage G3a, G3b and G4.

Study design

The trial will be a prospective, randomized, open, controlled design that will last 4 months. The trial was registered in the clinicaltrials.gov registry (ClinicalTrials.gov identifier: NCT03344549).

Study population

A total of 53 adult volunteers with a diagnosis of DKD will be recruited for this study. To be eligible in the trial, subjects must fulfil all of the inclusion criteria and none of the exclusion criteria, as stated below.

The following inclusion criterio will be adopted:

- (1) Outpatients aged 18–80 years.
- (2) With DKD with eGFR <60 ml / min / 1.73m² and ≥ 15 ml / min / 1.73m², (stage G3a, G3b and G4 respectively).
- (3) Written informed consent to participate in this study before any study-mandated procedure.
- (4) Who have access to the internet and have a computer, tablet or smartphone.
- (5) A willingness and motivation to follow the study protocol.

The exclusion criteria will be as follows:

[figure not shown]
- (1) Outpatients who have received prior nutritional treatment for the control of diabetic kidney disease.
- (2) The use of food supplements and / or keto analogues.
- (3) Diagnosis of anemia or recent transfusions (in the last 3 months).
- (4) With serious complications (chronic infection, septicemia, cancer, HIV, Alzheimer's, uncontrolled heart failure, liver failure, refractory arterial hypertension, etc.).

[figure not shown]

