The detection of patients is carried out in the nephrology department of the Juan I. Menchaca hospital, both in the morning and afternoon sessions. The identification of patients is carried out during the consultation with the nephrologist, where the selection criteria are evaluated and the patient is invited to participate in the study and to sign the agree consent.

After the patient's acceptance to participate in the study, the initial evaluation is carried out, which includes contact, demographic, anthropometric and dietary data; and the patient is trained to fill the dietary record at home. Anthropometric data are evaluated by standardized nutritionist trained with the correct technique. Venous blood was collected by qualified nurses. The biochemical indicators are requested by the nephrologist at the time of the consultation and the results of these are obtained from the institution's own data system.

After the initial evaluation, the probabilistic group assignment is carried out with the simple method without replacement, which is carried out using a sealed envelope. After the appointment of the group, the patient is scheduled for his first nutrition consultation (both arms).

In the teleconsultation group, two days before the first nutrition consultation, the patient is advised by telephone - or the family member in charge - about the use of the free technological tool to be used during the video conference.

In the patients of the intervention group, the nutritional intervention is carried out through teleconsultation with the free technological tool chosen (the patients from home and the

nutritionist from the remote clinic); and the patients of the control group are offered the nutritional intervention through face-to-face consultations carried out by the nutritionist of the nutrition service of the institution. All patients will be confirmed by phone the date and time of their next nutrition consultation, both the control group and the intervention group (Table.1)

Table 1. Timeline of the study

Time (weeks) from start of dietary intervention	Pre- baseline	Study period						Close- out
		Baseline	(I1)	(I2)	(I3)	(I4)	(I5)	
		(I0)	Week -1	Week 0	Week 4	Week 8	Week 12	Week 16
Screening and sign the agree consent.	x							
Randomization	x							
Socio- demographic data	x							
Blood serum measurements	x							x

Dietary habits	x						x
Anthropometric measures	x						x
Nutritional intervention		x	x	x	x	x	
Level of compliance			x	x	x	x	

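### Change in HbA1c and eGFR is compared with no baseline covariate although both baselines are measured: valid, but less precise than ANCOVA where the t-test or group-by-time test applies

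*Combined protocol and SAP*

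**What the plan says.** Under Data Analysis Principles, "the following changes from the baseline (I1) to the end of the study (I6) will be determined as primary outcomes"; the two outcomes listed are eGFR and HbA1c. Table 1 marks "Blood serum measurements" before the intervention and again at close-out. Data collection lists HbA1c and serum creatinine. Each patient who completes therefore has a baseline and a final value for both outcomes.

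The Statistical Analysis Plan names three kinds of between-group method that could bear on a continuous outcome:

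- Continuous variables "were compared using Student’s t-test or the Mann–Whitney U test, respectively", the choice resting on a Shapiro-Wilk test.
- For variables with several time points, "repeated measures analysis of variance tests were used for the comparisons between groups".
- For interaction or intervening variables, "a stratified statistical analysis will be carried out, using contingency tables and the Mantel-Haenszel method".

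No ANCOVA, regression or continuous baseline covariate appears. The plan does not say which test is primary for the two changes. The sample size section states: "A size of 27 patients per group was estimated, considering an expected difference in the Glycated Hemoglobin percentage of 0.7". It gives no SD, power or baseline-final correlation.

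**The concern.** A change is one number per patient, so it falls most naturally under the t-test/Mann-Whitney sentence. The ANOVA sentence may be meant for "Level of compliance", which Table 1 shows at four visits. If it also covers HbA1c and eGFR, defining the outcome as a change points to the group-by-time term. With two time points that is the same test as the t-test on change (F = t²). Mantel-Haenszel works on categorical tables and does not adjust a continuous outcome. On either parametric reading the baseline enters only by subtraction, which fixes its coefficient at 1 instead of estimating it.

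What is at stake is the width of the confidence interval, and the power, for both primary comparisons in a trial of 53 patients. The baseline that would help is already collected.

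**Working it through.** **Inputs from the documents.** 26 and 27 patients (N = 53); two-sided alpha 0.05; HbA1c difference 0.7; 27 per group; eligible eGFR from 15 to below 60 ("With DKD with eGFR <60 ml / min"). **Assumed, because not given:** the SD, the design power, r, and k = final SD / baseline SD.

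**1. The plan's own figure.** The 27 per group cannot be reproduced without an SD and a power. Solved backwards, SD = 0.7·√(27/2)/(1.960 + z_power), which is 0.918 at 80% power and 0.793 at 90%. So 27 is not shown to be wrong.

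**2. Variances.** With baseline SD s and final SD ks:

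- Var(change) = s²(1 + k² − 2rk)
- Var(ANCOVA) = s²k²(1 − r²)
- Difference = s²(1 − rk)², never negative

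Against the change-score t-test, ANCOVA can therefore lose only the cost of estimating one slope. At N = 53 that is a variance factor of 1 + 1/49 = 1.0204. With t on 50 instead of 51 df (squared ratio 1.00097), the worst CI-width ratio for any r and k is √(1.0204 × 1.00097) = 1.011.

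**3. Size of the gain.** The variance ratio is k²(1 − r²)/(1 + k² − 2rk), which is (1 + r)/2 at k = 1. The last two columns include the small-sample cost; equivalent N = 53/[1.0204(1 + r)/2].

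| r | ratio, k=0.9 | ratio, k=1 | ratio, k=1.1 | CI-width ratio, k=1 | equivalent N, k=1 |
|---|---|---|---|---|---|
| 0.3 | 0.58 | 0.65 | 0.71 | 0.815 | 80 |
| 0.5 | 0.67 | 0.75 | 0.82 | 0.875 | 69 |
| 0.7 | 0.75 | 0.85 | 0.92 | 0.932 | 61 |
| 0.8 | 0.79 | 0.90 | 0.97 | 0.959 | 58 |
| 0.9 | 0.81 | 0.95 | 1.00 | 0.985 | 55 |

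These figures need no SD or design power. The ANCOVA interval is the wider one only for r > 0.958 (k = 1), r from 0.827 to 0.953 (k = 1.1) and r from 0.734 to 0.898 (k = 1.2); never at k = 0.9.

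**4. HbA1c power** (noncentral t, 26 vs 27, difference 0.7). With SD of change 0.918 the change score has 78%. ANCOVA at r = 0.3/0.5/0.7/0.8/0.9 has:

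- k = 0.9: 94/91/88/86/85%
- k = 1: 92/88/83/81/79%
- k = 1.1: 89/85/80/78/77%

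With SD of change 0.793 and k = 1 it is 88% against 97/95/92/91/89%. If 0.918 is instead the single-visit SD (k = 1), then at r = 0.3/0.5/0.7/0.8 the change score has 63.3/77.7/94.0/99.0% and ANCOVA 80.6/87.5/96.5/99.4%.

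**5. eGFR.** Assume baseline SD 45/√12 = 13.0 (uniform over the eligible range). The 95% CI half-width, change score vs ANCOVA, at r = 0.7, 0.8, 0.9 is:

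- k = 1: 5.55 vs 5.17, 4.53 vs 4.35, 3.20 vs 3.16
- k = 1.1: 5.87 vs 5.69, 4.81 vs 4.78, 3.44 vs 3.47

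Eligibility truncates baseline eGFR, so k above 1 is plausible there.

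**6. Validity.** In normal-data simulation (20,000 trials per cell; k = 0.9 to 1.2, r = 0.3 to 0.9), type I error was 0.046 to 0.053 for both methods in every cell.

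**7. The full planned rule, with its Mann-Whitney branch.** Simulated with 26 vs 27 patients, SD of change 0.918, k = 1, normal baseline and 6,000 runs per cell. The shape of the final-value residuals is an assumption. Power, planned rule vs ANCOVA:

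| Residuals | r=0.3 | r=0.7 | r=0.8 | r=0.9 |
|---|---|---|---|---|
| Normal | 78 vs 91% | – | 78 vs 82% | 78 vs 79% |
| Laplace | 80 vs 91% | 82 vs 84% | 84 vs 82% | 84 vs 79% |
| t, 3 df | 85 vs 92% | 90 vs 86% | 92 vs 85% | 92 vs 83% |

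Lognormal residuals (log SD 1) gave 95 vs 89% at r = 0.5 and 99 vs 85% at r = 0.8. A separate run agreed: at r = 0.8, 91 vs 85% for t with 3 df and 99 vs 83% for lognormal.

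**The case against.** The strongest objection is that the plan does not commit to a t-test. It switches to Mann-Whitney when Shapiro-Wilk rejects. A reader might infer from the 1% bound that ANCOVA can never do materially worse than the plan as written. The documents do not support that: the rank test is one of the planned analyses, and step 7 shows it ahead by 2 to 14 points or more for heavy-tailed or skewed data at r of about 0.7 to 0.9. This objection stands, and it limits the point to the t-test and its group-by-time equivalent.

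Four smaller objections:

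- **The largest gain sits at the lowest r tried.** True. At r = 0.8 to 0.9 with k = 1 the HbA1c gain is 1 to 3 points of power, and for eGFR there may be none. The range should be read as a whole.
- **Fixing the SD of change while r varies shifts the population.** Also true: the implied single-visit SD, 0.918/√(2(1 − r)), runs from 0.78 at r = 0.3 to 2.05 at r = 0.9. The plan does not say which SD it used. The width ratios and equivalent N do not depend on this.
- **The primary test is inferred.** It is, and the plan should name it. Neither parametric reading uses the baseline as a covariate, so the inference does not decide the point.
- **It may be too late.** The methods are partly in the past tense. That changes how the ANCOVA must be labelled, not whether it is informative.

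**Conclusion.** The point holds as a matter of precision, at the level of a change that should be made. A reader might infer that leaving out the baseline biases the comparison; under randomisation it does not, and simulated error rates are nominal. No error-rate harm is claimed for the Shapiro-Wilk switch either.

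Against the t-test on change or the group-by-time test, ANCOVA at N = 53 with k = 1 narrows the interval by about 18% at r = 0.3, falling to 1.5% at r = 0.9. It widens it by at most about 1% for any r and k. The possible gain exceeds the possible loss in that comparison only. HbA1c, on which the sample size rests, benefits if its r is moderate; eGFR may gain nothing if its r is high. No superiority over the Mann-Whitney branch can be claimed for markedly non-normal data. Confidence is medium, because r, k, the SD and the shape of the data are all assumptions.

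**What to change.** - For each primary outcome, replace the t-test (or group-by-time ANOVA) with an ANCOVA of the end-of-study value on group plus the pre-intervention value marked in Table 1. Report the adjusted mean difference with its 95% CI.
- Where the planned rule would go to Mann-Whitney, report a rank-based test beside the ANCOVA, preferably a baseline-adjusted one (rank ANCOVA). Do not claim that ordinary ANCOVA is more powerful there.
- If repeated-measures ANOVA is kept for these outcomes, state that group-by-time is the treatment test. The group main effect would be a poor substitute: simulated power for the 0.7 difference was 52/34/21/10% at r = 0.3/0.5/0.7/0.9.
- If outcome data have already been examined, report the ANCOVA as post hoc beside the planned tests.

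**Cost.** No patients, visits or assays. One degree of freedom: at worst about 1% in CI width (about 1 point of power) against the t-test. Against the rank test, power may be lost if the data are markedly non-normal, which is why that test stays in the report. If the data are unseen, this is a wording change to the Statistical Analysis Plan; if not, it is a disclosed additional analysis.

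### Repeated-measures ANOVA of the compliance score, in its classical form, would drop patients the plan retains; a mixed model using every available rating should replace it

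*Combined protocol and SAP*

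**What the plan says.** The Statistical Analysis Plan section assigns a method by type of variable: "For variables measured at multiple time points, repeated measures analysis of variance tests were used for the comparisons between groups". It does not name compliance in that sentence. It identifies the software ("Statistical analysis and graphics were performed with IBM® SPSS® Statistics Ver. 22") but not the procedure within it.

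Under Data Analysis Principles, adherence is the only secondary outcome: "Level of compliance, was assessed using a self-reported Likert scale", scored from 1 (poor) to 10 (good). In Table 1 the row "Level of compliance" carries four marks and the nutritional intervention row five. Blood, diet and anthropometry carry two each. Compliance is therefore the only tabled outcome with more than two measurements, and the one to which the sentence most naturally applies.

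Two attendance rules are given, and they disagree:

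- The reasons for discontinuation list "Non-attendance at the study visits (≥ 2 nutritional interventions", so a patient with one missed consultation stays in.
- Dietary Interventions says, for each arm, "Failure to attend more than two consultations is considered an exclusion criterion", so a patient with two missed consultations stays in.

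The documents contain no missing-data rule, imputation method, mixed model or definition of the analysis population.

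**The concern.** Classical repeated-measures ANOVA needs a complete set of scores from each patient. A patient with three of four ratings contributes nothing. The attendance rules deliberately keep patients with one or two missed consultations, so partial records are to be expected, and the named method has no use for them.

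Two things are at stake. The first is precision: ratings already collected are discarded in a trial of 53 patients. The second is bias. Missing a consultation is plausibly a sign of lower adherence, so deletion may depend on the outcome being compared. The arms attend in different ways, by video from home or in person at the hospital, so attendance could differ between them. If both hold, the arm with more missed visits loses more of its less adherent patients and looks better than it is.

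**Working it through.** **Inputs from the documents.** 26 and 27 patients allocated, 53 in all (Randomization); five consultations and four compliance ratings (Table 1, whose columns are misaligned in the text available, so the marks are counted and not placed); the two attendance rules quoted above. The plan gives no figure for compliance to reproduce. Its 27 per group concerns HbA1c and does not bear on this point.

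**Assumed inputs.** Each consultation is missed independently with probability m, and a missed consultation means a missing rating. The documents state neither. The values m = 5%, 10% and 20% show a range.

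**Step 1: patients with all four ratings.** P(complete) = (1 − m)^4.

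- m = 5%: 0.95^4 = 0.815; 53 × 0.815 = 43.2 patients.
- m = 10%: 0.90^4 = 0.656; 53 × 0.656 = 34.8.
- m = 20%: 0.80^4 = 0.410; 53 × 0.410 = 21.7.

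**Step 2: patients the plan retains, out of five consultations.**

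- Discontinue at two or more missed: R1 = (1 − m)^5 + 5m(1 − m)^4.
- Discontinue at more than two missed: R2 = R1 + 10m²(1 − m)^3.

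**Step 3: share of retained patients dropped.** Anyone with all four ratings has missed at most one of the five consultations and is retained under either rule. The share dropped is therefore 1 − P(complete)/R.

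| m | Complete, of 53 | Retained, two-or-more rule | Dropped | Retained, more-than-two rule | Dropped |
|---|---|---|---|---|---|
| 5% | 43.2 | 51.8 | 16.7% | 52.9 | 18.5% |
| 10% | 34.8 | 48.7 | 28.6% | 52.5 | 33.8% |
| 20% | 21.7 | 39.1 | 44.4% | 49.9 | 56.5% |

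The share of collected ratings thrown away is 1 − (1 − m)^4/(1 − m) = 1 − (1 − m)^3: 14.3%, 27.1% and 48.8%.

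**Step 4: precision.** In an illustrative simulation (score SD 1.5, within-patient correlation 0.5, 10% missed in both arms, no link to adherence), the standard error of the arm difference was 0.40 with complete cases. It was 0.34 using the available ratings of patients with at most one missing.

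**Step 5: bias.** Simulated trials had 26 and 27 patients, no true arm difference, between-patient SD 1.5, within-patient SD 1.2, and 5% versus 15% of ratings missed at average adherence. The log-odds of a miss rise by a chosen amount per SD of lower adherence. The difference is the arm with fewer misses minus the arm with more, so a negative value flatters the arm that misses more.

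| Link (log-odds per SD) | Complete-case bias |
|---|---|
| 0 | about 0 |
| 0.25 | about −0.14 |
| 0.5 | about −0.25 |
| 1.0 | about −0.4 |

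With 5% versus 10% missed and a link of 0.25, the bias is about −0.07. With equal miss rates it is about zero at every link tried.

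At the strongest link, about −0.2 remains if available ratings are used only from patients with at most one missing. Likelihood-type weighting of every available rating from all randomised patients leaves about 0 to −0.08 over the links tried.

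**The case against.** The strongest reply is that the plan nowhere says incomplete patients are deleted. Deletion is inferred from the usual form of the named method. The software also offers a mixed-model procedure, and the plan does not say which procedure is meant. That stands as a limit on the claim. It does not answer it, because the text names an ANOVA and provides nothing for partial records. If a mixed model was intended, the correction is a sentence.

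Second, a missed consultation need not mean a missing rating. The score is self-reported, patients are telephoned to confirm appointments, and the documents do not say whether a rating can be taken at another time or a visit rebooked. This stands: the figures are conditional on that link.

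Third, a reader might infer that the adherence comparison would be confined to patients with perfect attendance. Table 1 does not support that. With five consultations and four ratings, a patient who misses only the consultation without a rating still has a full set.

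Fourth, a reader might take a bias of about 0.4 points as the expected error. The documents give no attendance data. That size needs unequal attendance together with a strong link to adherence, and it is no larger than the illustrative standard error of 0.40. The supportable statement is a range that includes zero.

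Finally, only one self-reported secondary outcome is involved. The primary outcomes, change in eGFR and in HbA1c, rest on blood scheduled at the start and the end.

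**Conclusion.** The point holds as a should-fix matter for the secondary outcome. The plan retains patients with partial compliance records and names a method that, in its classical form, cannot use them. At assumed miss rates of 5% or 10%, about 43 or 35 of 53 patients would be analysed, and 17–18% or 29–34% of retained patients dropped, depending on the attendance rule. This rests on independent misses and on each missed consultation costing a rating. With no missed ratings, nothing is lost.

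Bias is possible but not demonstrated. It requires attendance that differs by arm and also depends on adherence. Under 5% versus 15% missed it runs from 0 to about 0.4 points in favour of the arm that misses more, and it is about zero if attendance is equal. The documents do not support saying that deletion is prescribed, or that bias of a known size is present.

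**What to change.** In the Statistical Analysis Plan, replace repeated-measures ANOVA for compliance with a likelihood-based linear mixed model. Use arm, visit and arm-by-visit as fixed effects, with a random patient effect or an unstructured covariance, and include every available rating from all randomised patients. Report the arm difference with its 95% CI, and tabulate the number of ratings obtained by arm and visit so that readers can judge the missingness.

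State that the model assumes ratings are missing at random. It reduces the bias described above but does not guarantee its removal, particularly as ratings may stop when a patient is discontinued. Say also whether a rating can be obtained when a consultation is missed. The two attendance rules contradict each other and must be reconciled.

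The cost is SAP wording only, with no new data; the stated software has a mixed-model procedure. The downside is reliance on the missing-at-random assumption.
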